The sample size was estimated assuming a 5% alpha error and 80% study power. The overall success rate after 1 year was 95% for chemo-mechanical caries removal,⁽³¹⁾ whereas it was 67% for traditional caries removal.⁽³²⁾ Based on the difference between independent proportions, the sample size was calculated to be 30 patients per group, increasing to 36 patients to make up for lost follow-up cases. Total sample = number per group x number of groups = 36 x 3 = 108 patients.

Software

The sample size was based on Rosner's method⁽³³⁾ calculated by G*Power 3.1.9.7. ⁽³⁴⁾

Eligibility criteria

The participants enrolled in this study will be selected after fulfilling the following criteria:

Inclusion Criteria

- Healthy children aged 8-10 years old.
- The presence of at least one deep carious class 1 lesion in the first permanent molar with a score of 5 or 6 according to the International Detection and Assessment System (ICDAS), detected by visual-tactile inspection to assess lesion severity. ⁽³⁵⁾ (APPENDIX I, Tables 1)

Exclusion criteria

- Children reporting spontaneous or elicited pain from caries or showing any signs of pulpal infection, swelling or abscess.
- Pulpal exposure or bleeding during the excavation procedure
- Children presenting with special health care needs or undergoing medical treatment for chronic or acute diseases affecting salivary flow.
- Allergy or sensitivity to any of the materials included in the study.

Randomization technique and allocation⁽³⁶⁾

- Subjects complying with the inclusion criteria will be randomly assigned to one of the treatment groups, using a computer-generated list of random numbers to either the Brix 3000, Papacarie duo gel group (www.random.org) or ART approach (Hand excavation).
- Allocation will be performed by a trial independent individual and the allocation ratio is intended to be equal (1:1:1).

Allocation concealment⁽³⁷⁾

An assistant will be responsible for giving each participant a serial number that will be used for his/her allocation. A duplicate of this number will be kept in an opaque envelope indicating to which group the patient belongs. This envelope will be kept by a trial independent individual who will be assigned the role of opening it only at the time of intervention; so that the group to which the child is allocated is concealed from the investigator. Grouping Participants will be randomly and equally allocated to one of the three treatment groups:

Grouping

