Participants will be randomly and equally allocated to one of the three treatment groups:

- Test group I (Brix 3000): 36 children meeting the eligibility criteria will be treated using Brix 3000.
- Test group II (Papacarie duo gel): 36 children meeting the eligibility criteria will be treated using Papacarie duo gel.
- Control group: 36 children will be treated using ART approach (Hand excavation).

Blinding⁽³⁸⁾

The investigator will not be blinded to the treatment type. However, the participants, the statistician, and the microbiologist will be blinded to the treatment group.

Materials

- BRIX 3000 gel. *
- Papacarie duo gel. **
- EQUIA Forte HT FIL glass ionomer capsules. ***

Materials for the microbiological assessment

- Mitis Salivarius Bacitracin (MSB) agar (selective culture media for *S. mutans*) prepared according* to the manufacturer's instructions. ****
- Rogosa SL agar plates (selective culture media for lactobacilli), prepared according to the manufacturer's instructions. *****
- Saline as a transport medium.
- Sterile test tubes.
- Sterile plastic Petri dishes.
- Anaerobic gas jar.
- Incubator. *****

* Brix Medical Science. Carcaraña, Santa Fe, Argentina.

** F&A Laboratório Farmacéutico Ltda, São Paulo, Brazil.

*** GC CORPORATION [name].

**** Difco Laboratories Inc, NJ, USA.

***** Himedia Laboratories, Mumbai, India.

***** Red line by binder.

Method

Training and calibration

The main researcher will be trained and calibrated by the study supervisors regarding the use of ICDAS criteria⁽³⁵⁾ in the diagnosis of the teeth to be included in the study, as well as application of both test materials.

Intra-examiner reliability ⁽³⁹⁾

The examination of 10 selected children between 8 to 10 years of age will be carried out followed by re-examination after seven days for the determination of intra-examiner agreement measured by Cohen's Kappa (K). Obtaining a Kappa score ≥ 0.8 is considered excellent reliability. These children will not be included in the study sample.

Baseline examination

- After obtaining the informed consent from the caregiver/parent, (APPENDIX II) the researcher will provide oral hygiene instructions to each of the study participants and will inform them about the importance of maintaining good oral hygiene and a proper diet guidance. ⁽⁴⁰⁾
- All the examinations and interventions will be done by one calibrated examiner.

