- No local anesthesia will be administered as it would alter the pain perception of the patient unless necessary.

Evaluations

1. Clinical evaluation

- The clinical assessment will be at 3-, 6- and 12-month intervals to evaluate
 - a) Postoperative pain
 - b) Any signs or symptoms of pulpitis
 - c) Vertical and horizontal percussion tests
 - d) Tooth-color alterations and fistulas presence.
 - e) Restoration success will be evaluated according to the criteria of atraumatic restorative treatment by Phantumvanit et al. (1996) (45). It is based on the retention of the material in the cavity and the presence of secondary caries.
 - f) Restorations which will receive a score of 0, 1 or 7 will be considered successful while those having a score of 2, 3, 4 or 8 will be considered failures. Those which will receive a score of 5, 6 will be excluded from the analysis (Appendix IV).

2. Radiographic evaluation

- Periapical radiograph will be taken immediately after clinical procedure and at 6- and 12-months intervals during follow up period to confirm the clinical evaluation.⁽⁴⁶⁾
- It will be obtained by the long cone paralleling technique to minimize the distortion using the film holders.⁽⁴⁷⁾
- The radiographic evaluation will be performed using the radiographic subtraction method and the assessment of the density of the remaining dentin by gray-scale analysis using the Image j 1.37 V program⁽³¹⁾.
- Therefore, a greater degree of density on the image will indicate a greater success.

- Any case that will exhibit pulp involvement associated with a radiolucent image or any signs for periapical lesions will be considered unsuccessful treatments.

3. Evaluation of time required to perform procedure

- The time needed for complete caries removal will be recorded for each caries removal method.
- The timing of each procedure will set immediately upon the first application by using a stopwatch and turned off when there is no carious dentin left in the cavity.
- After complete removal of decay, the teeth will be restored with glass ionomer filling as a temporary restoration to be replaced after the follow up period using Composite filling sandwich technique.

4. The participants' pain assessment:

- Subjective pain will be assessed after caries removal by means of Wong-Baker faces scale⁽⁴⁸⁾. It consists of faces with different facial expression for happiness and pain and is scored from 0-5 as 0 is very happy and feels no pain and 5 is very painful (APPENDIX III).

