- 1- Clinical effectiveness of each material during the follow up period at 3-, 6- and 12-months intervals confirmed with radiographic findings at 6- and 12-month intervals.
- 2- Timing required for complete caries removal following each caries removal method
- 3- Participants' subjective pain reaction following each caries removal method.
- 4- Antimicrobial effect of both CMCR agents by comparing the colony forming units (CFU) at the treatment visit before and after application of each agent compared to conventional caries removal method.

Follow up

All patients will be recalled after 3-, 6- and 12-month intervals. On the day of the recall appointment, patient preparation will be done as mentioned before.

Outcome assessment

- 1- Restorations which will receive a score of 0, 1 or 7 will be considered successful while those having a score of 2, 3, 4 or 8 will be considered failures.
- 2- Any clinical sign and symptoms teeth with pain, intraoral or extra oral abscess formation and fistula formation will be recorded as unsuccessful treatments
- 3- Any periapical lesions on radiography during follow-up will be recorded as unsuccessful treatments.

Study Plan

[figure not shown]

Figure 1: Flow chart of the study plan

STATISTICAL ANALYSIS

The statistical Package for Social Sciences (SPSS)* version 27.0 for Windows will be used for data analysis.

All data will be collected; The Chi square test will be used to compare the difference between the three groups regarding the clinical success, the T-test or the Mann-Whitney U test will be used to analyze the differences between the microbiological samples. The data will be graphically presented with suitable graphs. The level of statistical significance will be set at 5%.

* SPSS Inc., Chicago, IL, USA

ETHICAL CONSIDERATIONS

1. The research protocol will be approved by the Research Ethics Committee of Alexandria University Faculty of Dentistry (IRB No. 001056 –IORG 0008839) prior to any research-related activities.
2. All research activities involving human subjects will abide by the Declaration of Helsinki⁽⁵³⁾ and other ethical guidelines adopted by the Research Ethics Committee of Alexandria University Faculty of Dentistry.
3. Benefits:
 - It will provide caries treatment for young permanent molars in children using minimally invasive atraumatic procedures.
 - It will allow overcoming the disadvantages of conventional treatment with local anesthesia

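### No masked assessment is planned for the primary clinical and radiographic outcome, although the investigator is unblinded and one examiner does all examinations and treatments; coding films and recall forms would close part of this gap cheaply.

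*Combined protocol and SAP*

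**What the plan says.** The primary aim is clinical and radiographic success of the two gels against hand excavation (Aim of the study). Three places bear on who judges it.

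- **Blinding:** "The investigator will not be blinded to the treatment type". The masked parties are the participants, the statistician and the microbiologist. No clinical or radiographic assessor is listed.
- **Baseline examination:** "All the examinations and interventions will be done by one calibrated examiner". No other examiner is named anywhere.
- **Evaluations, item 2:** "The radiographic evaluation will be performed using the radiographic subtraction method", with gray-scale density as a further measure. No reader is named, and no coding of films is described.

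Success is judged at 3, 6 and 12 months clinically and at 6 and 12 months on radiographs. Under Evaluations, Outcome assessment and Appendix IV, restoration codes 0, 1 and 7 are successes and 2, 3, 4 and 8 are failures. Pain, abscess, fistula or a periapical lesion also makes the treatment unsuccessful. Training and calibration covers caries scoring by ICDAS and application of the gels. It does not mention the restoration codes or film reading.

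**The concern.** Several success/failure boundaries are matters of degree. A slight marginal defect (code 1, success) lies next to a defect of 0.5 to 1.0 mm (code 2, failure), and slight wear (code 7, success) next to wear above 0.5 mm (code 8, failure). Percussion response, colour change and early periapical signs also leave room for interpretation. A scorer who knows the arm may resolve doubtful cases differently by arm without intending to.

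A difference created in this way looks like a treatment effect. A larger sample does not dilute it, and no analysis can remove it afterwards. The plan masks the microbiologist, who serves a secondary aim, but provides nothing comparable for the primary one.

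**Working it through.** **The plan's own figure.** Inputs from Sample size estimation: alpha 0.05, power 0.80, and success of 0.67 with the traditional method; for the gels, "The overall success rate after 1 year was 95% for chemo-mechanical caries removal". Sidedness is not stated; two-sided is assumed. With mean proportion (0.95 + 0.67)/2 = 0.81, the pooled formula gives

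n = [1.96·√(2·0.81·0.19) + 0.8416·√(0.95·0.05 + 0.67·0.33)]² / 0.28² = (1.087 + 0.436)² / 0.0784 = 29.6, so 30 per group.

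This matches: "the sample size was calculated to be 30 patients per group, increasing to 36 patients to make up for lost follow-up cases". Power is 80.5% at 30 and 87.4% at 36; the implied loss is 1 − 30/36 = 16.7%. The point therefore does not turn on the sample size, and masking would not change it.

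**Illustration of unmasked scoring.** Assumptions, none of them from the documents: true success s is equal in all arms, and a fraction q of all gel failures is scored as success. Recorded success is then s + q(1 − s) in each gel arm and s in the hand-excavation arm. Statistical analysis names a chi-square test across the three groups at 5%:

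X² = Σ(xᵢ − n·m)² / [n·m·(1 − m)], with m = (x₁ + x₂ + x₃)/(3n), significant above 5.99 (2 degrees of freedom).

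The false-positive rate is the summed probability of all significant outcomes of three binomial counts. It is shown at 30 per arm (expected to be evaluable) and 36 per arm (enrolled).

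| True success s | q | Recorded gel success | Rate at 30 | Rate at 36 |
|---|---|---|---|---|
| 67% | 0 | 67% | 5.2% | 5.1% |
| 67% | 1 in 10 | 0.67 + 0.10·0.33 = 70.3% | 6.0% | 6.0% |
| 67% | 1 in 4 | 0.67 + 0.25·0.33 = 75.25% | 10.6% | 11.7% |
| 80% | 0 | 80% | 4.9% | 5.2% |
| 80% | 1 in 4 | 0.80 + 0.25·0.20 = 85% | 7.5% | 8.8% |
| 90% | 0 | 90% | 4.0% | 4.7% |
| 90% | 1 in 4 | 0.90 + 0.25·0.10 = 92.5% | 4.7% | 5.6% |

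Simulation of the 67%, 1 in 4 case gave 10.5% and 11.6%, in agreement. In that case the number of teeth recoded is small: 36 × 0.33 × 0.25 ≈ 3 per gel arm.

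**Can the arm be hidden?** Every tooth is restored with glass ionomer, and Materials lists one product, so the filling should give little away at recall or on the film. Allocation concealment already provides a trial-independent person who holds the envelopes. Two features limit what coding can do. Subtraction compares films of the same tooth, so pairing and order must stay visible. And the serial number is the allocation key (Allocation concealment) and is accessible to the principal investigator (Ethical considerations, item 5), so a form showing only that number would hide little from anyone with access to the key.

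**The case against.** The strongest reply is that parts of this are inference. The one-examiner sentence stands under Baseline examination and may have been meant for that visit only. It does say all examinations, and no one else is named, so extending it to the recalls is reasonable, but it is not spelled out. A reader might go further and infer that the operator reads the radiographs. The documents do not support that as fact: the radiographic section describes a technique and names no reader. What stands is that no masked reader is provided for.

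A reader might also infer that the result will be biased towards the gels. The PICOT question asks whether the gels do better, and the listed benefits include supporting their use. That shows an expectation, not how doubtful teeth will be scored.

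On size, q was applied to all failures, yet a missing restoration, a defect above 1.0 mm, an abscess or a fistula is hard to score as a success. Large values of q are therefore implausible. Pairwise tests give more striking figures: at 36 per arm, 67% success and 1 in 4, 12.3% per gel and 20.2% for either gel, against 5.4% and 9.7% without bias. But the only test named for clinical success is the three-group one, and much of the either-gel figure is multiplicity.

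Finally, a form cannot make an operator forget a child, and the budget has no line for a second examiner. That is correct for the clinical half. Films can be read masked whatever the reader remembers of the child.

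**Conclusion.** The point holds as a gap in the design. An unblinded investigator, a single examiner and an outcome that needs judgement leave the primary comparison without any masked assessment. The reading that the operator scores the recalls is well supported; the reader of the films is unspecified.

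The size is conditional. Under the assumptions above, the false-positive rate roughly doubles at 67% true success if 1 in 4 gel failures is upgraded, rises modestly at 80%, and is not materially inflated at 90% or when only 1 in 10 is upgraded. The fraction and the direction are unknown, so these figures show sensitivity and do not predict bias. The reading that full masking is available at almost no cost is not supported either: the radiographic outcome can be masked well, the clinical outcome only in part. The change is a cheap improvement that should be made before outcome data are collected; the gap does not invalidate the trial.

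**What to change.** 1. **Films.** For the outcome analysis, give each tooth's film set a random code that hides the arm but keeps the films paired and in time order for subtraction. Pool the three arms and read the sets in random order, by the examiner or a supervisor already on the trial. Keep the planned reading at each recall, where the 6- and 12-month films serve to confirm the clinical findings, separate from this masked reading.
2. **Recall forms.** Use forms that show neither the arm nor the allocation serial number, for example with a separate recall code. Enter the restoration code before any treatment record is opened. The trial-independent person keeps the key until the data are locked.
3. **Blinding section.** Name who scores the recalls and who reads the films. State that radiographic outcome reading is masked and that clinical scoring is only partly masked.

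The cost is protocol wording, clerical coding and a second reading of the films. Sample size, visits and staff do not change. The remaining weakness is that the operator may remember some children; this should be reported as a limitation.

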Heading out of the contradictory results, no publication has reported the in vivo comparison between Papacarie duo and the newly developed CMCR agent Brix 3000 gel in terms of their clinical and radiographic success and their antimicrobial effect compared to the Art approach for caries removal in young immature permanent teeth. The null hypothesis of this study is that no statistically significant difference will be detected between both materials and ART approach regarding to their clinical performance, and their antimicrobial effect in young permanent molars during the follow up period.

AIM OF THE STUDY

Primary aim

- To assess and compare the effectiveness of two chemo-mechanical agents Brix 3000 and Papacarie duo in terms of their clinical and radiographic success in young permanent molars, in comparison with ART approach.

Secondary aims

- Determine the required time for complete caries removal for each method.
- Evaluation of patients' subjective pain reactions following each method.
- Evaluation of antimicrobial effect of two chemo-mechanical caries removal agents by comparing the colony forming units (CFU) at the treatment visit before and after the application of each agent compared to hand excavation method.

MATERIALS AND METHODS

Study design

This will be a randomized, parallel, three-arms controlled clinical trial, with a 1:1:1 allocation ratio. It will be set up and reported according to the CONSORT guidelines.⁽³⁰⁾

The PICOT question is:

Will children (8-10 years old) with class I carious lesion in the first permanent first molar (with ICDAS score 5 or 6) (population; P) using Brix 3000 or Papacarie duo gel (intervention; I) for Chemo-mechanical caries removal in comparison with ART approach (Hand excavation) (Control; C) show a greater success (outcome; O) at different time intervals over twelve months period (time; T)?

Study setting and location

The study will take place in the Department of Pediatric Dentistry and Dental Public Health at the Faculty of Dentistry and the Department of Microbiology and Immunology at the Faculty of Pharmacy, Alexandria University, Alexandria, Egypt.

Sample

Sample size estimation

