- Periapical x-ray radiographs will be taken for each tooth before enrolling it into the trial to determine that the carious lesion depth does not involve the pulp.

Intervention

- All the lesions in the children's oral cavity indicated for treatment will be treated and sampled for microbiological analysis prior to and following caries removal.
- On the day of the intervention, the children will be asked to refrain from tooth brushing in the morning, as well as eating and drinking (except water) for at least two hours before the appointment. ⁽⁴¹⁾

- The patients will be instructed to rinse with a cup of water, then the outer surface of the carious lesion will be washed with a flurry of water to avoid contamination of plaque bacteria. ⁽⁴²⁾
- The tooth will then be partially isolated using cotton rolls and saliva ejector.
- Two portions of dentin will be collected with sterile excavators from the middle of the cavity to perform the microbiological analysis of each tooth before and then after caries removal procedure. ⁽⁴¹⁾
- The dentin sample will then be inserted in a sterile test tube containing 1 mL of saline and transported to the microbiology laboratory within 1-2 hours. ⁽⁴³⁾
- Dentin sample weight will be calculated by measuring the difference between the weight of the whole set (sterilized bottle and transporting medium) and the previously determined weight of the set without dentin. ⁽⁴⁴⁾
- The bacterial count obtained for a given amount of dentin will be used to estimate the number of colonies present in 1 mg dentin (CFU/mg). ⁽⁴⁴⁾
- **In the CMCR group:** either Papacarie duo or Brix 3000 gel will be applied on the carious lesion of tooth and left undisturbed for 30-60 seconds, following manufacturer instructions ⁽²⁸⁾. This produces softening of carious dentin, which will be removed with a hand excavator. This step will be repeated 2-3 times until dentin demonstrates slight resistance with no tug-back sensation when tested with an exploratory probe while pressing an explorer into dentin, then the application of the chemo-mechanical agents will be stopped.
- The visual test for assessment of complete caries excavation will be based on non-turbid appearance of the CMCR agent used.
- **In the ART group** hand excavation will be performed to remove the carious tissue from the cavity by using a sterile sharp hand excavator. The cavity will be determined to be caries-free according to visual and tactile clinical criteria.

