- Each child will be trained to use the scale by first modeling and then asking each participant to think of the last time she/he felt something painful' and to select the facial expression that best represented his/her experience of discomfort.

5. Microbiological evaluation Procedure

- Samples from the carious lesion will be collected prior to and following complete caries removal for detection of the change in bacterial count (Streptococci and Lactobacilli counts).

a. Sample dilution

All samples will be dispersed by vortexing for 30 seconds then 10-fold serially diluted using sterile saline. A measure of the dilution will then be used for traditional plate culturing methods. ⁽⁴⁹⁾

b. Culture

Aliquots of 10 ml of each dilution will be inoculated into freshly prepared Rogosa agar media using a micropipette.

- Mitis Salivarius agar plates will be incubated anaerobically in an atmosphere containing 10% CO₂ at 37°C for 72 hours to detect Streptococcus mutans count
- Rogosa agar plates will be incubated aerobically at 37° C for 48 hours to detect Lactobacilli count.

c. Isolation and Enumeration

Following the predetermined incubation period, colonies grown on the specified media will be counted and represented as (CFU/ml). Streptococcus mutans will be identified based on their characteristic morphology on Mitis Salivarius agar plates. Similarly, Lactobacilli will be identified biochemically and microscopically on the basis of their morphology.

Colony count

The number of colonies will be determined and expressed as colony forming units using the following equation. ⁽⁵⁰⁾

$$\text{CFU/ml} = \frac{\text{n}^\circ \text{ of colonies} \times \text{dilution factor}}{\text{Volume taken in ml}^{(51)}}$$

6. Oral Health quality of life questionnaire

- Oral health quality of life will be assessed at one week recall appointment by using the Arabic validated version of the child perceptions questionnaire. ⁽⁵²⁾
- It consists of 25 items distributed among 4 domains: oral symptoms, functional limitations, emotional well-being, and social well-being. It is self-reported by children using a 5-point Likert scale (APPENDIX V), and responses range from 0–4 for each item. Hence, total scores range from 0 to 100, and higher scores indicate poorer OHRQoL. (APPENDIX VI)

STUDY OUTCOME

Treatment effect will be evaluated after the follow up period by comparing:

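### Bacterial counts are sampled from every treated lesion, but the named tests need independent observations and no unit of analysis is stated

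*Combined protocol and SAP*

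**What the plan says.** **Unit of design.** Randomisation is of subjects, and the Grouping section puts 36 children in each arm. Under Sample size estimation, "the sample size was calculated to be 30 patients per group", raised to 36 for loss to follow-up.

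**Bacterial counts, a secondary aim.** The Intervention section says "All the lesions in the children's oral cavity indicated for treatment will be treated and sampled for microbiological analysis". It adds that dentin is collected "to perform the microbiological analysis of each tooth before and then after caries removal procedure". Neither sentence restricts sampling to class I lesions of first permanent molars. The Microbiological evaluation Procedure section uses the singular: "Samples from the carious lesion will be collected prior to and following complete caries removal".

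**Analysis.** The STATISTICAL ANALYSIS section says "the T-test or the Mann-Whitney U test will be used to analyze the differences between the microbiological samples". It does not say whether the t-test is paired or unpaired, or whether the comparison is between arms or before against after. For clinical success it says "The Chi square test will be used to compare the difference between the three groups regarding the clinical success".

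**Eligibility.** A child needs "The presence of at least one deep carious class 1 lesion in the first permanent molar". No maximum is set, and there is no rule for choosing among several eligible molars.

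No section names an index tooth, a unit of analysis, a within-child summary or a method for clustered data.

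**The concern.** A t-test or Mann-Whitney U test treats each observation as independent; a paired t-test treats each pair as independent. Two lesions in one mouth share the child's diet, saliva and flora, and are treated in the same arm, so their counts are likely to be correlated. If every sampled lesion becomes a row in the analysis:

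- the standard error is too small and the nominal 5% test rejects too often;
- children with more lesions get more weight;
- lesions that would not qualify for the trial can enter the CFU comparison.

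For clinical success the question is whether the chi-square test has one row per child or one per tooth. The plan leaves this open, so the unit could be settled after results are known.

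**Working it through.** **1. The plan's own sample size.** Inputs from Sample size estimation: 95% and 67% success, alpha 5% (two-sided assumed), power 80%. The mean proportion is (0.95 + 0.67)/2 = 0.81.

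n = [1.96·√(2·0.81·0.19) + 0.8416·√(0.95·0.05 + 0.67·0.33)]² / 0.28² = (1.0874 + 0.4362)² / 0.0784 = 29.6, rounded up to 30.

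The stated 30 reproduces exactly; power at 30 is 80.5%. This calculation has one result per patient and no allowance for clustering.

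**2. Effect of pooling lesions in the CFU test.** Lesions per child and the ICC are not in the documents, so both are assumptions. If a fraction f of children have two lesions and the rest one, the variance of a naive comparison is understated by the design effect

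DE = 1 + 2f·ICC/(1 + f),

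and the actual two-sided error is 2·[1 − Φ(1.96/√DE)].

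| Children with two lesions | ICC | DE | Actual error |
|---|---|---|---|
| 20% | 0.1 | 1.033 | 5.4% |
| 20% | 0.3 | 1.100 | 6.2% |
| 20% | 0.5 | 1.167 | 7.0% |
| 50% | 0.1 | 1.067 | 5.8% |
| 50% | 0.3 | 1.200 | 7.4% |
| 50% | 0.5 | 1.333 | 9.0% |
| All | 0.1 | 1.100 | 6.2% |
| All | 0.3 | 1.300 | 8.6% |
| All | 0.5 | 1.500 | 11.0% |

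Example, all children with two lesions and ICC 0.3: DE = 1 + 2·1·0.3/2 = 1.3; 1.96/√1.3 = 1.719; error 8.6%.

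Simulation with 30 children per arm (normally distributed change, unpaired t-test) agrees to within about 1 percentage point. A paired before-after t-test within one arm gives nearly the same range: 5.3% to 6.9% at 20%, and 6.4% to 10.8% if all have two. Mann-Whitney on the change gives 5.2% to 7.3% and 6.4% to 11.0%.

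**3. More than two lesions.** The Intervention wording has no cap. With m lesions in every child, DE = 1 + (m − 1)·ICC. Simulated t-test error is 12.2% at m = 3, ICC 0.3, and 22.1% at m = 4, ICC 0.5.

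**4. Where there is no inflation.** With one lesion per child, or ICC 0, DE = 1 and the error is about 5%. A before-after test that ignores the pairing need not be inflated either: its variance ratio is (1 − r)·DE, where r is the before-after correlation. With r = 0.5 and DE = 1.5 this is 0.75, below 1.

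**5. Clinical success: the text side by side.** Towards the tooth: entry requires one lesion or more, the Baseline examination section describes the tooth as what is enrolled, and success is scored per restoration with no rule for combining several. Towards the child: the sample size is in patients, the arms are in children, and the PICOT question speaks of a "class I carious lesion in the first permanent first molar". The text does not settle it.

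**6. Check of a child-level summary.** Taking one mean change per child in the scenarios of step 2 (10,000 simulated trials each), the t-test error was 4.7% to 5.5%.

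**The case against.** The strongest reply is that one tooth per child was always meant. Randomisation, arm sizes and sample size are all in children, the PICOT question and the microbiology section use the singular, and the 30 per group reproduces with one result per child. It is also true that the plan nowhere says samples will be treated as independent. That follows only from the tests named, with nothing alongside them to handle several lesions in a child. If nearly every child has one sampled lesion, the effect is negligible.

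Much of this stands, and it limits the point. It does not remove it, because the Intervention section plainly has all lesions sampled, and no section says how to get from there to one value per child.

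Three stronger readings are tempting, and the documents do not support them:

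- *The clinical success analysis is invalid.* The text is ambiguous, and the patient-based design leans towards one result per child. Inflation would arise only if several teeth per child entered the chi-square test.
- *The trial is too small because clustering was ignored.* The calculation is in patients and stands with one result per child.
- *The error rate is 20% or more.* That needs about four lesions in every child and a high ICC; the documents give no figure for either.

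**Conclusion.** The point holds for CFU, a secondary outcome: the sampling sentence and the named tests do not fit together, and the Intervention and microbiology sections disagree on what is sampled. Under a literal reading, a between-group or paired test has a type I error of about 5-7% if 20% of children have two lesions, and about 6-11% if all do. It is higher with more lesions. These figures assume an ICC of 0.1 to 0.5. Separately, lesions outside the eligibility criteria could enter the CFU data. For clinical success the finding is an unstated unit, not a demonstrated error. A change should be made before analysis; confidence is moderate because the intent may well have been one tooth per child.

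**What to change.** 1. Reconcile the Intervention and Microbiological evaluation Procedure sections on which lesions are sampled and which samples are analysed.
2. State that the child is the unit of analysis for CFU and clinical success, and that only eligible class I first permanent molars enter the main analysis.
3. Pre-specify one index molar per child, chosen at random among the eligible ones and recorded before the allocation envelope is opened, analysed with the planned tests. For CFU, one mean change per child over the eligible molars is an acceptable alternative.
4. Label all other sampled teeth as supportive only.

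The cost is a few sentences in Methods and in the statistical section. Extra teeth then add little or nothing to the main analysis. Because pulpal exposure during excavation is listed as an exclusion, an index molar may be lost in a child who has another eligible molar; the plan should say beforehand how the analysis treats that child. The 30 (36 with loss to follow-up) children per group need no change. If one tooth per child was always intended, this only writes it down.
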